## 4.3.3. Clinical Laboratory Parameters

Summary statistics will be presented for laboratory measurements (hematology and chemistry) overall for all patients in the SAF Population. Urinalysis results will be presented in a listing. The following analytes will be tabulated/listed:

- **Hematology**: complete white blood cell count with differential, hemoglobin, hematocrit, and platelets.
- **Serum chemistry profile**: albumin, alkaline phosphatase, alanine aminotransferase (ALT), amylase, aspartate aminotransferase (AST), blood urea nitrogen, calcium, chloride, creatine phosphokinase, creatinine, direct bilirubin, gamma glutamyl transferase, glucose, lactate dehydrogenase, lipase, lipid profile (total cholesterol, highdensity lipoprotein, low-density lipoprotein, and triglycerides), magnesium, phosphorus, potassium, sodium, total bilirubin, total protein, and uric acid. In addition, eGFR will be presented using the following formula: eGFR = 1.86 x [Creatinine/88.4]-1.154 x [Age]-0.203 x [0.742 if female] x [1.210 if Black].

Urinalysis results will be presented in a data listing and will include results from microscopic testing only. Pregnancy test, Serum Follicle-Stimulating Hormone (FSH) test, Hepatitis Serology, C-reactive Protein, and Viral Resistance Testing will also be presented in a data listing only.

Normal ranges for the laboratory parameters will be provided by the laboratory that performed the assessments. All normal ranges will be standardized and results will be reported in standard units. The tables will include summary statistics for the Baseline assessments and the changes from Baseline to each subsequent time point of measurement. A listing of patients with abnormal (i.e., outside normal range) laboratory assessments will also be presented.

Potentially Clinically Significant (PCS) criteria may be applied to laboratory parameters as clinically indicated, and if applied, will be summarized as described above. PCS is defined as a laboratory value that is lower or higher than a laboratory's normal range limits.

Note: Electronic clinical laboratory data will be received at Westat. Data reconciliation will be performed to resolve any discrepancies with the Oracle database. Details of data receipt will be described in the Data Receipt Plan.

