An increase in the mean number of CD4+ T-cells of 63 cell/ μ L was observed from Baseline to Week 25. This increase in CD4+ T-cells is indicative of the therapeutic effect over 24 weeks. At Week 25 after treatment with the 800 mg a 2wk maintenance dose, the mean change in viral load from Day 7 was 1.6 log₁₀ reduction with 55% and 48% of patients having a $\geq 1 \log_{10}$ and $\geq 2 \log_{10}$ reduction, respectively. Viral load < 50 and < 200 HIV-1 RNA copies/mL was reached in 43% and 50% of patients, respectively.

The most common adverse reactions (all Grades) reported in at least 5% of subjects were diarrhea, dizziness, nausea, and rash. Table 1 shows the frequency of adverse reactions occurring in 5% or more of subjects.

Table 1. Adverse Reactions (All Grades) Reported in $\geq 5\%$ of Subjects Receiving ibalizumab and Optimized Background Regimen for 23 Weeks in Trial TMB-301

	Percent of All TMB-301 Subjects (N=40) n (%)
Diarrhea	3 (8%)
Dizziness	3 (8%)
Nausea	2 (5%)
Rash*	2 (5%)

*Includes pooled terms “rash”, “rash erythematous”, “rash generalized”, “rash macular”, “rash maculopapular”, and “rash papular”

Most (90%) of the adverse reactions reported were mild or moderate in severity. Two subjects experienced severe adverse reactions: one subject had a severe rash and one subject developed immune reconstitution inflammatory syndrome manifested as an exacerbation of progressive multifocal leukoencephalopathy.

Laboratory Abnormalities

Table 2. Selected Laboratory Abnormalities (\geq Grade 3) in Trial TMB-301

	% Subjects N=40
Bilirubin ($\geq 2.6 \times$ ULN)	5%
Direct Bilirubin ($>$ ULN)	3%
Creatinine ($>1.8 \times$ ULN or $1.5 \times$ baseline)	10%
Blood Glucose ($>$ 250 mg/dL)	3%
Lipase ($>3.0 \times$ ULN)	5%
Uric Acid (>12 mg/dL)	3%
Hemoglobin ($<$ 8.5 g/dL)	3%
Platelets ($<$ 50,000/mm ³)	3%
Leukocytes ($<$ 1.5 10^9 cells/L)	5%
Neutrophils ($<0.6 \times 10^9$ cells/L)	5%

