5.1 Inclusion Criteria

Patients may be enrolled in Cohort 1 if they meet both of the following criteria:

1. Are currently receiving ibalizumab via other TaiMed-sponsored or Investigator-sponsored IND protocol
2. Are capable of understanding and have voluntarily signed the informed consent document

Patients may be enrolled in Cohort 2 if they meet all of the following criteria:

1. Are 18 years of age or older
2. Are capable of understanding and have voluntarily signed the informed consent document
3. Have documented HIV-1 infection by official, signed, written history (e.g., laboratory report); otherwise, an HIV-antibody test will be performed
4. Are able and willing to comply with all protocol requirements and procedures
5. Have a viral load >1,000 copies/mL and documented resistance to at least one antiretroviral medication from each of three classes of antiretroviral medications as measured by previous resistance testing (resistance testing is not provided by the study for qualification purposes)
6. Have a history of at least 6 months on antiretroviral treatment
7. Are receiving a failing antiretroviral regimen OR have failed and are off therapy
8. Have viral sensitivity/susceptibility to at least one antiretroviral agent other than ibalizumab, as determined by previous resistance test performed within 6 months prior to Screening and be willing and able to be treated with at least one agent to which the

patient's viral isolate is fully sensitive/susceptible according to the Screening resistance tests as a component of the OBR

9. If sexually active, are willing to use an effective method of contraception during the study and for 30 days after the last administration of the study drug

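### The eGFR formula in SAP 4.3.3 has a leading constant of 1.86, so it returns about 0.8 for a patient with normal creatinine and makes every planned eGFR summary about 100 times too small

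*SAP*

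**What the plan says.** SAP section 4.3.3 lists the serum chemistry analytes and then adds a derived variable: "eGFR will be presented using the following formula: eGFR = 1.86 x [Creatinine/88.4". The creatinine ratio is raised to the power -1.154 and age to the power -0.203 ("1.154 x [Age] -0.203", where the superscripts are flattened in the text). The last terms are the multipliers "0.742 if female] x [1.210 if Black".

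The section gives no unit for creatinine or for eGFR; it says only that "results will be reported in standard units". SAP section 4.2 defines age in years. For the laboratory tables, section 4.3.3 states: "The tables will include summary statistics for the Baseline assessments and the changes from Baseline to each subsequent time point of measurement".

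The formula appears once. Nothing else in the SAP or protocol restates it, gives a different constant, or defines an eGFR unit or reference range.

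**The concern.** The divisor 88.4 converts creatinine from umol/L to mg/dL, so a creatinine of 1.0 mg/dL makes that term equal to 1. What remains is the constant times a power of age that is below 1 for any adult. With a constant of 1.86 the result cannot approach a normal GFR. The printed value looks like a misplaced decimal point.

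Safety and tolerability are primary objectives in both cohorts (protocol section 2.1), and renal function is a natural place for a reader to look. In the protocol's TMB-301 table of "Selected Laboratory Abnormalities" (section 1.2, Table 2), creatinine has the highest rate of the ten Grade 3 or higher abnormalities listed: 10% of 40 patients. An eGFR table that follows the SAP would show apparent end-stage renal failure in patients with normal kidneys. Any cut-off later applied to it would have no meaning.

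**Working it through.** **Inputs from SAP 4.3.3.** Constant k = 1.86; creatinine Cr divided by 88.4; exponents -1.154 (creatinine ratio) and -0.203 (age); 0.742 if female; 1.210 if Black.

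**Assumptions.** Creatinine is in umol/L, as the divisor implies. The ages and creatinine values are illustrative; the documents give only the lower age limit for Cohort 2 ("Are 18 years of age or older"). An eGFR of 60 to 120 is taken as plausible for a man with creatinine 1.0 mg/dL. The documents contain no worked eGFR value to reproduce, so the check evaluates the formula directly.

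**Formula.** eGFR = k x (Cr/88.4)^-1.154 x age^-0.203 x [0.742 if female] x [1.210 if Black]

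**Reference case: Cr 88.4, age 50, non-Black man**
- (88.4/88.4)^-1.154 = 1
- 50^-0.203 = 0.452
- eGFR = 1.86 x 1 x 0.452 = **0.84**

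**Other patients, all at Cr 88.4 umol/L**

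| Patient | k = 1.86 | k = 186 |
|---|---|---|
| Age 30, non-Black man | 0.93 | 93.3 |
| Age 50, non-Black man | 0.84 | 84.1 |
| Age 50, non-Black woman | 0.62 | 62.4 |
| Age 50, Black man | 1.02 | 101.7 |
| Age 50, Black woman | 0.75 | 75.5 |
| Age 70, non-Black man | 0.79 | 78.5 |

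**Range over creatinine and age**
- Non-Black men: 1.68 at (53 umol/L, age 30) and 0.35 at (177 umol/L, age 70).
- With the formula's own multipliers, the upper end is 1.68 x 1.210 = 2.04 (Black man) and the lower end is 0.35 x 0.742 = 0.26 (non-Black woman).
- Over creatinine 45 to 120 umol/L and ages 18 to 70, both sexes and both race terms: 0.41 to 2.73.

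**Creatinine needed to reach eGFR 60 (age 50, non-Black man)**
Cr = 88.4 x [60 / (1.86 x 0.452)]^(-1/1.154) = about 2.2 umol/L, roughly one fortieth of 88.4.

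**Constant needed for a plausible result (reference man)**

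| Target eGFR | k = target / 0.452 | Ratio to 1.86 |
|---|---|---|
| 60 | 133 | 71 |
| 90 | 199 | 107 |
| 120 | 266 | 143 |

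A shift of two decimal places gives 186, exactly 100 times the printed value and inside this range.

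**Could other units rescue 1.86?**
- *Result per second.* The reference man's value would be 0.841 x 60 = 50.4 per minute, still below the assumed 60 to 120, and the SAP declares no such unit. A constant of 186 expressed per second would be 186/60 = 3.1, not 1.86.
- *Creatinine entered in mg/dL.* At 1.0 mg/dL the formula gives 1.86 x (1/88.4)^-1.154 x 0.452 = 148. At 2.0 mg/dL it gives 148 x 2^-1.154 = about 67. The divisor would then have no purpose, and a doubled creatinine would still return a value above 60.

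**The case against.** The strongest counter-argument concerns importance. eGFR is an added, descriptive variable. It feeds no endpoint, eligibility criterion, withdrawal rule or toxicity definition, and SAP section 3.4.2 plans no formal hypothesis testing. Serum creatinine is tabulated in its own right in the same section, so the kind of signal seen in TMB-301 would remain visible. A 100-fold error would probably be noticed in the first output. All of this is true. It limits the damage but does not make the formula usable.

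Some narrower points also stand:
- A value below 1 describes a typical patient, not every patient with normal creatinine. A 50-year-old non-Black man passes 1 once creatinine falls below about 76 umol/L. Values up to 2.73 are still far too low.
- No eGFR threshold is planned, and the potentially clinically significant criteria are optional, so any harm through flags is conditional.
- The documents show that the constant is far too small but do not by themselves prove that it must be 186.
- Percent changes would be unaffected, but the section plans changes from Baseline, which scale with the constant.
- The program may already use another constant. In that case the code and the SAP disagree, and the SAP still needs correcting.
- A stray decimal point in the electronic text cannot be fully excluded; the SAP page itself settles that.

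**Conclusion.** The formula is wrong as written. With creatinine in umol/L, no realistic adult input gives a usable GFR: the reference patient gets 0.84, and the ranges examined never exceed 2.73. The mean, standard deviation, median, minimum, maximum and absolute change all scale linearly with the constant, so every planned eGFR statistic would carry the same error if the program follows the text.

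The factor is exactly 100 if the intended constant is 186. From the assumed plausible eGFR of 60 to 120 alone, it is 71 to 143. The conclusion rests on reading 88.4 as a conversion from umol/L; the alternative unit readings do not give a coherent formula. The error is confined to one derived safety variable, but that variable cannot be reported as specified, so it should be corrected before any output is produced.

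**What to change.** In SAP section 4.3.3:
- Change the leading constant from 1.86 to 186, after confirming it against the sponsor's own source for the equation, and cite that source.
- State the units: creatinine in umol/L, age in years, result in mL/min/1.73 m2.
- Add one worked check value to the programming specification: creatinine 88.4 umol/L, age 50, non-Black man, eGFR about 84.
- Check the existing program against that value.

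The cost is one number and a line of text in the SAP, plus one constant in the program if it follows the current text. No data collection or other analysis changes, and there is no downside.

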3.6 Safety Assessments

Safety assessments will include the results of the following measurements throughout the study:

- Physical examinations
- Vital sign measurements
- Clinical laboratory parameters (hematology, serum chemistry, and urinalysis)
- Monitoring of AEs and concomitant medications
- Incidence of Class C events as defined by the Centers for Disease Control and Prevention (CDC) Classification System for HIV Infection (Appendix A)
- Anti-ibalizumab antibody levels (immunogenicity of ibalizumab)

4. Study Treatments

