7.2.2 Clinical Laboratory Parameters

Collection of blood and urine samples for clinical laboratory assessments will be part of a normal safety profile assessment for the study patients. Patients need not fast before blood sampling. Samples will be processed using standard procedures as described in the laboratory procedures manual and will be analyzed by a central laboratory unless otherwise noted.

The samples will be analyzed for the following:

- **Hematology:** complete white blood cell count with differential, hemoglobin, hematocrit, and platelets
- **Serum chemistry profile:** albumin, alkaline phosphatase, alanine aminotransferase (ALT), amylase, aspartate aminotransferase (AST), blood urea nitrogen, calcium, chloride, creatine phosphokinase, creatinine, direct bilirubin, gamma glutamyl transferase, glucose, lactate dehydrogenase, lipase, lipid profile (total cholesterol, high-density lipoprotein, low-density lipoprotein, and triglycerides), magnesium, phosphorus, potassium, sodium, total bilirubin, total protein, and uric acid
- **Urinalysis:** visual inspection for appearance and dipstick assessment for color, pH, specific gravity, ketones, protein, glucose, bilirubin, nitrite, urobilinogen, and leukocyte esterase

The urinalysis will be performed at the site by qualified personnel. If the results of the urinalysis are abnormal, a urine sample will be sent to the central laboratory for microscopic evaluation. Samples will be processed as described in the laboratory procedures manual before being sent to the central laboratory for evaluation.

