9.7.2 Clinical Safety Laboratory Parameters

Clinical laboratory parameters will be presented by visit. Descriptive statistics will be used to summarize observed values by visit as well as the change from Baseline at each visit. Clinical laboratory values outside the normal ranges will be flagged in patient data listings. Non-numeric data will be presented in patient data listings, but will not be tabulated.

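### SAP 4.3.3 limits the urinalysis listing to reflex microscopy, so the routine dipstick results that the protocol schedules are neither listed nor summarized

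*SAP*

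**What the plan says.** **Collection.** Protocol 7.2.2 defines urinalysis as "visual inspection for appearance and dipstick assessment for color, pH, specific gravity, ketones, protein, glucose, bilirubin, nitrite, urobilinogen, and leukocyte esterase". Site staff perform it. Microscopy is conditional: "If the results of the urinalysis are abnormal, a urine sample will be sent to the central laboratory for microscopic evaluation". The opening of Protocol section 7 states the same rule. In the schedule tables, urinalysis shares a row with hematology and serum chemistry, so it is due at every clinical laboratory visit.

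**Reporting in the protocol.** Protocol 9.7.2 says "Clinical laboratory parameters will be presented by visit" and "Non-numeric data will be presented in patient data listings, but will not be tabulated".

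**Reporting in the SAP.** Section 4.3.3 first says "Urinalysis results will be presented in a listing", with no restriction. It then says "The following analytes will be tabulated/listed", and the bullets that follow cover hematology and serum chemistry only. After those bullets comes the restriction: "Urinalysis results will be presented in a data listing and will include results from microscopic testing only". Two general SAP rules point the other way. Section 3.4.1 puts individual patient data in listings, and section 4.3 repeats the protocol's rule on non-numeric data.

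**The concern.** The listed result exists only when the unlisted one was abnormal. A listing built this way is selected on outcome. It contains no normal urinalyses, and it shows that something was abnormal without showing the protein, glucose or other reading that prompted the microscopy.

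Safety and tolerability are a primary objective in both cohorts, and the study has no control group, so a reviewer depends on reading each patient's results over time. The protocol's own summary of TMB-301 reports Grade 3 or higher creatinine in 10% of 40 patients, that is 0.10 × 40 = 4. Dipstick protein is a collected urine result that could help in reading a creatinine or eGFR change. At stake is whether that reading is available beside the serum values. This does not presume that the drug caused the creatinine findings.

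**Working it through.** There is no power, alpha or event figure to reproduce. The check compares the texts and counts visits.

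**1. What is scheduled.** Counted from the hematology, chemistry and urinalysis row of the schedule tables, for a patient who completes:

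| Schedule | Visits with urinalysis | Count |
|---|---|---|
| Cohort 2, Table 3-5 | Screening, Day 0, Day 7 | 3 |
| Cohort 2, Table 3-6 | Weeks 12, 24, 28, 36, 48, 60, 72, 84, 96, 120, 150 | 11 |
| Cohort 2 total | | 3 + 11 = 14 |
| Cohort 1, either dosage (Tables 3-1 to 3-4) | Screening/Day 0; Weeks 12, 24, 36, 48, 60, 72, 96, 120, 150 | 1 + 9 = 10 |

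The visit lists in Protocol 6.1 to 6.3 agree. A footnote to one of the SAP's mock laboratory listings says that Cohort 1 had no laboratory samples at TMB-311 Screening. If that is so, the Cohort 1 count is 10 − 1 = 9.

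**2. What would be listed.** Let r be the number of microscopy results for a Cohort 2 completer. The listing has entries for r visits and nothing for the other 14 − r. With r = 2, for illustration, 12 visits are empty. Each empty visit could be a normal dipstick, a urinalysis not done, or an abnormal dipstick whose reflex sample was not processed. The output looks the same in all three cases, so it supplies no denominator for an abnormality rate. The documents give no rate of abnormal dipsticks, so r cannot be estimated.

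**3. Which rule each reading falls under.**
- If a dipstick item is numeric (pH, specific gravity), Protocol 9.7.2 has it presented by visit.
- If it is non-numeric, Protocol 9.7.2 and SAP 4.3 have it listed.
- Either way, SAP 3.4.1 has individual patient data listed.
- Under the microscopy sentence in SAP 4.3.3, neither kind appears.

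**4. Which SAP sentence would govern.** A programmer would normally follow the specific sentence in 4.3.3 over the general ones in 3.4.1 and 4.3.

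**5. Whether the departure is declared.** SAP 4.5.2 openly says that it departs from the protocol on which patients the secondary endpoints cover. SAP 4.3.3 contains no such statement and gives no reason for the limit.

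**The case against.** A reader might infer that dipstick results never reach the safety report. The documents do not support that:
- Protocol 8.2 has clinically significant laboratory findings recorded as adverse events, and these enter the TEAE tables in SAP 4.3.2.
- An abnormal dipstick leads to microscopy, and a listed microscopy result shows indirectly that the dipstick was abnormal.
- SAP 3.4.1 and 4.3, read alone, would list the dipstick data.

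These points stand, but they leave a gap. Under Protocol 8.3 a laboratory change counts as an adverse event only if judged clinically significant, and a value explained by a diagnosis is not recorded separately. Drift below that threshold is not shown. Microscopy does not identify the dipstick item that was abnormal.

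A reader might also infer a breach of Protocol 3.6. That section names urinalysis as a safety assessment but sets no output format; only 9.7.2 bears on reporting.

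Nor does the plan abandon renal safety. SAP 4.3.3 tabulates creatinine and blood urea nitrogen with change from Baseline, and adds eGFR. Serum glucose is tabulated too. Dipstick readings are supplementary to these. The 4 of 40 figure comes from a single-arm study on background antiretrovirals, with a threshold that also admits a rise to 1.5 times baseline.

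Finally, a new table of worsening dipstick protein or glucose may be tempting. Protocol 9.7.2 and SAP 4.3 both say that non-numeric data are not tabulated, so the documents support a listing and no more.

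**Conclusion.** SAP 4.3.3 is wrong as written, with a modest consequence. It limits the urinalysis output to a test done only after an abnormal dipstick, so the scheduled results (14 per Cohort 2 completer, 10 per Cohort 1 completer) are neither listed nor summarized under that rule. This contradicts Protocol 9.7.2 and the SAP's own general rules, and it is not declared.

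The counts measure scheduled collection; they do not estimate missed safety signals. The primary effectiveness endpoint and the serum laboratory and adverse event summaries are untouched.

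The conclusion assumes that the specific sentence in 4.3.3 governs over 3.4.1 and 4.3. The mock layout of the urinalysis listing was not available to check. If it carries dipstick columns, the text of 4.3.3 still has to be brought into line with it.

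**What to change.** In SAP 4.3.3, end the restricting sentence at the data listing and delete the clause that confines its content to microscopy. Then state that the listing shows each dipstick item by patient and visit, with abnormal values flagged and microscopy results alongside where they were triggered. A scheduled visit with no dipstick entry will then mean that no result was recorded. No added table is needed. If the sponsor prefers to keep the restriction, the SAP should declare it as a departure from Protocol 9.7.2 with a reason, and reconcile SAP 3.4.1 and 4.3 with it.

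The cost is a change to one sentence and one longer listing. This assumes that the site dipstick readings are in the EDC system, as Protocol 10.1 requires of all data. That section does not show how much detail is captured, so the fields should be confirmed before programming.

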Tests with Grade 3 or Grade 4 abnormal results should be repeated within 72 hours of the site becoming aware of the abnormal value(s). See Appendix B for details and definitions of toxicities. The Principal Investigator should discuss any Grade 3 or 4 abnormal laboratory results with the medical monitor/Sponsor for appropriate patient disposition, including potential withdrawal from the study (see [Section 5.3.1](#) for additional information). Per [Section 5.3.1](#), the study treatment should be stopped for all Grade 3 or 4 treatment-related laboratory abnormalities, as defined in Appendix B. Any patient with a Grade 3 or Grade 4 laboratory abnormality that resolves before the next scheduled dose may have the study drug reinstated. If a patient develops a persistent Grade 3 or Grade 4 treatment-emergent laboratory abnormality, excluding triglycerides and cholesterol, that does not resolve prior to the next scheduled study drug administration, study drug may be discontinued. Patients with Grade 3 or 4 triglyceride and/or cholesterol elevations are allowed to continue to receive study drug.

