 For TMB301 Rollovers, BASELINE is the value recorded on Day 7 of the TMB-301 study. For TMB202 Rollovers, BASELINE is the value recorded on Day 0 of the TMB-202 study. Lab samples were not collected at the TMB-311 Screening for the Cohort 1 patients. EOS=End of Study visit conducted at Week 96.

 $\label{lem:westat} \begin{tabular}{ll} $\tt Created on DDMMYYYY) \\ {\tt S:\TMB311\DA\SAS\L\_LABOTH.SAS} \end{tabular}$ 

 L = Below lower limit of normal; H = Above upper limit of normal.

 Potentially Clinically Significant is defined as having a result either below the lower limit of normal or above the upper limit of normal.

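### The SAP's potentially clinically significant laboratory label means the same as abnormal, and the visible SAP text specifies no laboratory summary by DAIDS grade

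*SAP*

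**What the plan says.** SAP 4.3.3 defines the category in one sentence: "PCS is defined as a laboratory value that is lower or higher than a" normal-range limit of the laboratory. Whether it is used is left open: "Potentially Clinically Significant (PCS) criteria may be applied to laboratory parameters as clinically indicated". If used, it is to be summarised in the same way as the other laboratory results.

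The same section also plans an output for abnormal values, defined by the same limits: "A listing of patients with abnormal (i.e., outside normal range) laboratory assessments will also be presented".

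In SAP Section 6, footnote [3] to a laboratory listing repeats the rule: "Potentially Clinically Significant is defined as having a result either below the lower limit of normal or above the upper limit of normal". Footnote [2] of that listing defines the L and H flags by the same two limits.

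The protocol works with graded severity. Its section 7.2.2 says "Tests with Grade 3 or Grade 4 abnormal results should be repeated within 72 hours". DAIDS Grade 3 or 4 also appears in the Cohort 2 exclusion criteria (5.2) and the withdrawal section (5.3.1). Table 2 in protocol section 1.2 reports the TMB-301 laboratory results at Grade 3 or higher.

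**The concern.** A label that speaks of clinical significance should tell the reader something that an out-of-range flag does not. Here it cannot, because the two rules are identical. The definition has no severity element, so a value just past a limit counts the same as a Grade 4 value. It has no baseline element either, so a patient who was out of range before ibalizumab and did not change is still labelled PCS.

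Demonstrating safety and tolerability is a primary objective for both cohorts. If the optional PCS summary is run as written, it will look like a count of important laboratory abnormalities but will be a count of out-of-range values. No other laboratory output described in the visible SAP text counts patients by severity of abnormality or by worsening from Baseline.

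**Working it through.** The plan states no flag rate, so there is no figure to reproduce. The redundancy follows from the text alone; the arithmetic only shows its possible scale.

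**The rules side by side**

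- Abnormal (SAP 4.3.3): outside the normal range.
- L/H flag (listing footnote [2]): below the lower or above the upper limit of normal.
- PCS (SAP 4.3.3 and listing footnote [3]): below the lower or above the upper limit of normal.

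Every abnormal value is PCS and every PCS value is abnormal, so the columns always agree.

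**Inputs for the illustration**

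- Chemistry analytes: 26, by counting the SAP 4.3.3 list, which ends "magnesium, phosphorus, potassium, sodium, total bilirubin, total protein, and uric acid".
- Hematology analytes: the SAP names "complete white blood cell count with differential, hemoglobin, hematocrit, and platelets". That is 4 items, or 9 if a five-part differential is assumed. Total k = 30 to 35.
- Post-baseline laboratory visits, Cohort 1: 9 (Weeks 12, 24, 36, 48, 60, 72, 96, 120, 150; protocol 6.1.3 and 6.2.3).
- Post-baseline laboratory visits, Cohort 2: 12 (Day 7 and Weeks 12, 24, 28, 36, 48, 60, 72, 84, 96, 120, 150; protocol 6.3.3 and 6.3.5 to 6.3.7).
- Assumption not in the documents: a share p = 5% of results falls out of range by chance, with 2.5% to 10% as the range shown.

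**One visit, independent analytes:** P(at least one flag) = 1 − (1 − p)^k.

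- p = 5%: 1 − 0.95^30 = 78.5%; 1 − 0.95^35 = 83.4%.
- p = 2.5%: 53.2% to 58.8%.
- p = 10%: 95.8% to 97.5%.

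**Allowing for correlation, p = 5%.** Each result is simulated as a standard normal value, flagged beyond ±1.96. It is the sum of a patient-level part, constant over visits, and a visit-level part. Both parts are equally correlated across analytes. The correlation of one analyte across visits is 0.5 or 0.8, with 10,000 simulated patients per setting. Ranges cover both values of k and both cross-visit correlations.

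| Correlation between analytes | One visit | Any of 9 visits | Any of 12 visits |
|---|---|---|---|
| 0 | 78.3% to 83.6% | 99.6% to 100% | 99.9% to 100% |
| 0.3 | 66.1% to 71.2% | 97.9% to 100% | 98.8% to 100% |
| 0.5 | 50.5% to 54.3% | 92.8% to 99.4% | 95.3% to 99.8% |

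**One analyte, p = 5%:** 5% at one visit. Over 12 visits, 1 − 0.95^12 = 46% if visits are independent, and about 19% to 32% with the cross-visit correlations above.

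For scale, Table 2 of the protocol gives Grade 3 or higher rates of 3% to 10% per parameter in TMB-301 (N = 40). Three of its four thresholds expressed against the upper limit of normal lie well above it (bilirubin 2.6 times, creatinine 1.8 times, lipase 3.0 times). Direct bilirubin is the exception, at the limit itself. Out-of-range and Grade 3 or higher are thus different measures for most of these parameters.

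**The case against.** A reader might infer that nearly every patient will be flagged and that the safety signal is lost. The documents do not support that reading.

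- PCS is optional, and the primary safety variables are AEs and discontinuations (Protocol Summary; protocol 3.2).
- Laboratory changes judged clinically significant are recorded as AEs (protocol 8.3), graded with reference to Appendix B (8.5) and tabulated by grade (SAP 4.3.2).
- Grade 3 or 4 results are retested and discussed with the medical monitor or sponsor (protocol 7.2.2).
- Change-from-Baseline statistics and the abnormal listing are planned separately, as protocol 9.7.2 asks. A graded table goes beyond that section.
- No laboratory comparison with TMB-301 is promised.
- The high flag rates count any analyte over the whole schedule, and the SAP describes no such patient count.
- The listing footnote shows that the definition is in place, not that a PCS table will be produced. The listing body and several mock pages are not available to check.

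All of this stands, and it limits the consequence. It does not rescue the definition. The discretion covers whether PCS is applied, while what it means is fixed. Nor do the other outputs supply a laboratory incidence summary. Visit means do not count patients with severe values. AE capture depends on investigator judgement and omits values explained by a recorded diagnosis (protocol 8.3). Retesting is a conduct rule, not an analysis.

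**Conclusion.** The point holds in a limited form. As written, PCS duplicates abnormal in SAP 4.3.3 and in the listing footnote, so any flag or summary built on it is uninformative about severity and about change on treatment. The visible SAP text specifies no DAIDS-graded laboratory summary; removed mock pages cannot be judged.

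The redundancy needs no assumption. The size does. It rests on a 5% chance rate, 30 to 35 analytes and assumed correlations, and it describes chance alone, not observed rates in these patients. On that basis, wide flagging is supported for any analyte over a patient's full follow-up, but not for a single visit once correlation is allowed for, and not analyte by analyte. This should be corrected before the laboratory outputs are produced, but it does not undermine the primary safety assessment.

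**What to change.** In SAP 4.3.3 and in the listing footnote:

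- Define PCS as a post-baseline value of DAIDS Grade 3 or 4 (protocol Appendix B) that is at least one grade worse than Baseline.
- Tabulate n (%) of patients by analyte in the Safety Population.
- Replace the optional wording with a statement that this summary will be produced.
- Keep the out-of-range flag, labelled as abnormal only.

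Two existing SAP rules carry over and should be stated with the table. Section 3.3.3 places Baseline for TMB-202 and TMB-301 rollover patients in the earlier study, so those values need grading too. Section 3.3.2 uses the original result at a visit in preference to a retest, so the count would include unconfirmed values.

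The cost is SAP wording and the programming of grades. Any analyte without a DAIDS grade stays in the abnormal listing; which ones cannot be checked here, because Appendix B is a separate document. No count under the new rule can be projected, since the documents give no graded rates for this study. The change concerns an analysis definition only and alters no clinical management rule.
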